**Sample Size**

Sample size was calculated for a study power of 80% and an alpha of 0.05. Event rate in the control group was estimated as 40%, while that in the treated group was considered 5%. The number of resulting patients in each group is 19 for a total sample of 38 patients. This assumes a significant impact of treatment on S-IRIS-KS occurrence and its mortality.

The antiretroviral scheme will be assigned according to the criteria of the “The Antiretroviral Management Guide of Persons with HIV” in effect in Mexico.

Candidates will have an initial thorough clinical evaluation including a work-up to diagnose coinfections and rule out other neoplasms that comprise: ophthalmologic evaluation, computed tomography (CT) scan (neck, thorax, and abdomen), bone marrow culture with bone biopsy, Hepatitis B Virus (HBV) and Hepatitis C Virus (HCV) serology, venereal disease research laboratory (VDRL) test and if indicated lumbar puncture to rule-out neurosyphilis, Histoplasma urinary antigen and serology, and GenXpert MTB/RIF test. Upper gastrointestinal tract (GIT) endoscopy with biopsy of lesions; colonoscopy will be performed only on patients with diarrhea or lower-GIT bleeding. Biopsies of enlarged lymph nodes will be obtained and processed for histopathological analysis and culture. If indicated, bronchoscopy with bronchoalveolar lavage (BAL) will be performed as well as a thoracic Gallium 67 Spect-CT Scan or PET-FDG scans.

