**Criteria for Non-severe-IRIS KS and Severe-IRIS-KS**

**Non-severe-IRIS-KS:** Is defined as an increase in the number of KS lesions plus  $\geq$ one log10 of HIV-1 RNA VL decrease or  $\geq$ 50 cells/mm^3 or  $\geq$ 2-fold from baseline CD4+ cells increase after cART initiation.

**Severe-IRIS-KS:** Is defined as an abrupt clinical deterioration after cART initiation alongside the presence of at least two clinical and at least three laboratory criteria.

Clinical criteria: 1) Fever (no identified concomitant infection), 2) increase in the size or number of KS lesions, 3) exacerbation of lymphedema, 4) appearance or increase of otherwise unexplained lung opacities on the chest images with a negative Gallium-Scan negative and 4) appearance or increase of pleural effusion.

Laboratory criteria: 1) Thrombocytopenia  $<$ 100,000 platelets/ml; 2) Anemia (decrease of at least 1 g/dl from previous measure and no obvious bleeding), 3) Hyponatremia  $<$ 135 mEq/L and 4) Hypoalbuminemia  $<$ 3.5 g/dL. This is the clinical picture associated with death.

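### The platelet criterion for severe IRIS is written per ml, 1,000 times lower than the same figure per mm3; the unit should be confirmed and the classified events checked against it

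*Protocol*

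**What the plan says.** The protocol section *Criteria for Non-severe-IRIS KS and Severe-IRIS-KS* requires, besides a sudden worsening once cART has begun, "at least two clinical and at least three laboratory criteria". Four laboratory criteria are listed:

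1. thrombocytopenia, with a cut-off of "100,000 platelets/ml";
2. "Anemia (decrease of at least 1 g/dl from previous measure and no obvious bleeding");
3. sodium below 135 mEq/L;
4. albumin below 3.5 g/dL (the list closes with "and 4) Hypoalbuminemia").

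In the same section, the non-severe definition states the CD4 rise in cells per mm3. No other part of the protocol restates the platelet criterion. The SAP uses S-IRIS-KS without redefining it, so this section is the only operative definition.

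The protocol's *Primary outcome* is death from any cause at 48 weeks. The SAP names death attributed to S-IRIS-KS as primary. It also analyses repeated S-IRIS-KS episodes and the number of participants with at least one.

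**The concern.** Two blood cell counts in one endpoint section use units that differ by a factor of 1,000. For platelets, the literal unit gives a cut-off so low that the criterion would in practice drop out. Because three of only four laboratory criteria are needed, losing one changes the rule materially: anemia, hyponatremia and hypoalbuminemia would all have to be present.

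This is a decision threshold, not background text. It enters the SAP's Cox analysis of S-IRIS-KS deaths, its Poisson analysis of episodes and its count of affected participants. The protocol's per-protocol analysis of S-IRIS-KS uses it too. The protocol's *Blinding* section says the study is open label, and neither document describes blinded adjudication. A laboratory rule that each assessor must silently reinterpret gives less protection against inconsistent classification than a laboratory rule should. With 19 patients planned per group, a few reclassified events could matter.

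**Working it through.** **The plan's own derived figure.** The platelet cut-off is a definition and cannot be reproduced from inputs. The only derived figure nearby is the sample size. Inputs from the protocol's *Sample Size* section are 40% against 5%, power 80% and alpha 0.05; sidedness is not stated and is taken as two-sided here. The unpooled normal approximation gives

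n = (0.40×0.60 + 0.05×0.95) × (1.96 + 0.8416)² / 0.35² = 18.42, rounded up to 19 per group.

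This matches the plan. The platelet unit does not enter the formula, so correcting it leaves 19 unchanged.

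**Unit conversion.** 1 ml = 1,000 mm3, so 100,000 per ml = 100,000 / 1,000 = 100 per mm3. Conversely, 100,000 per mm3 = 100,000,000 per ml. The factor is exactly 1,000.

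**Effect on the laboratory rule.** Four yes/no criteria with at least three met give five qualifying patterns: four with exactly three met and one with all four. If the platelet criterion is never met, one pattern remains, namely the other three together.

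**Direction.** Any count below 100 per mm3 is also below 100,000 per mm3. Every event that qualifies under the literal unit therefore also qualifies under the per-mm3 unit. A literal reading can remove severe events but cannot add any.

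**Size, as illustration only.** The documents give no frequency for any criterion. Assume the criteria are independent, the other three each have probability p, and platelets under the per-mm3 reading have probability q:

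- four working criteria: p³ + q × 3p²(1−p)
- literal reading: p³
- share lost: 1 − (literal / four criteria)

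| p | q | four criteria | literal | share lost |
|---|---|---|---|---|
| 0.3 | 0.3 | 8.4% | 2.7% | 68% |
| 0.5 | 0.5 | 31% | 12.5% | 60% |
| 0.7 | 0.7 | 65% | 34% | 47% |
| 0.7 | 0.2 | 43% | 34% | 20% |
| 0.7 | 0.6 | 61% | 34% | 44% |
| 0.9 | 0.9 | 95% | 73% | 23% |
| 0.9 | 0.2 | 78% | 73% | 6% |
| 0.9 | 0.6 | 88% | 73% | 17% |

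For example, at p = 0.9 and q = 0.2: 0.729 + 0.2 × 3 × 0.81 × 0.1 = 0.7776, and 1 − 0.729/0.7776 = 6%. The shares lost run from about 6% to 68%, depending entirely on the assumed probabilities.

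**The case against.** The strongest reply is that this is an obvious slip with no practical effect. The criterion is labelled thrombocytopenia, CD4 cells appear per mm3 a few lines earlier, and an infectious diseases specialist examines patients at each visit. Such an assessor would very probably read the figure per mm3, and if all did so, no event changes. Nothing in the documents shows that anyone applied the literal unit. A micro sign lost when the PDF was read also cannot be fully excluded, although the Greek gamma elsewhere in the protocol survived. All of this stands. It lowers the likely impact but does not make the text correct.

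A reader might infer three stronger things, and the documents support none of them.

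- *That half to two thirds of severe events are lost.* That range comes from giving all four criteria the same probability between 0.3 and 0.7. Other choices, equally arbitrary, give far less. Independence is doubtful too, since the abnormalities may well cluster in one deterioration.
- *That the control event rate would fall below the planned 40%.* The documents do not say how the 40% was obtained or with what unit. The SAP labels that event only as IRIS, while the protocol's *Sample Size* section speaks of S-IRIS-KS.
- *That the trial's main result is compromised.* The protocol's all-cause mortality outcome does not use this criterion. The protocol's secondary count combines severe and non-severe events, so a downgraded case with more lesions and the required viral-load or CD4 response would still be counted there.

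**Conclusion.** The definition is wrong as written, by an exact factor of 1,000, and neither document corrects it. Read literally, three of four laboratory criteria becomes three of three, and severe events could only be lost. This step rests on one assumption from general knowledge: that a platelet count below 100 per mm3 is in effect never seen. How many events would be lost cannot be estimated from the documents; the 6% to 68% range is illustrative.

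The likeliest explanation is a unit slip that assessors read per mm3, in which case the effect on results is nil. The point still merits action, because the threshold determines the S-IRIS-KS counts and S-IRIS-KS deaths in the SAP, and the documents do not show which unit was applied. It does not touch all-cause mortality or the 19 per group.

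**What to change.** - The sponsor checks the source page and confirms the intended platelet unit.
- The unit is corrected in the endpoint definition (per mm3, that is per microlitre, if that was intended), in the protocol and in any case-definition form.
- The sponsor verifies that every event in both arms was classified with that same unit, and records the result. Any event classified otherwise is reclassified and the S-IRIS-KS analyses rerun.

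The cost is one unit in the text and a check of the classified events in a planned sample of 38 patients.

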### **Classification of KS evolution:**

**Complete Response (CR):** when all of the KS lesions disappear, according to physician's criteria documented by pictures taken in each visit.

**Partial Response (PR):** when there was a diminution of >50% in number and/or size of original lesions without the appearance of new lesions, according to physician's criteria documented by pictures taken in each visit.

**Stable Disease (SD):** was when there was a reduction of <50% of lesions and new lesions have not appeared, according to physician's criteria documented by pictures taken in each visit.

**Disease Progression (DP):** when an increase is documented of the number and size of the KS lesions during follow-up periods.

**Relapse:** when new lesions appeared in patients with CR or documented CR in previous evaluations.

Visits will be performed at baseline, week 1, 2, 4, 8, 12, 16, 24, and 48. At each visit, an Infectious Diseases specialist will perform a clinical evaluation, and pictures of skin lesions will photograph. Blood samples will be obtained for: WBC count, complete blood chemistry, urine analysis, CRP, D-Dimer, HIV VL with Abbott Real-time, HHV-8, CMV, and Epstein-Barr Virus (EBV) VL ELITE MGB KIT by ELITE InGenius Software, CD4+ and CD8+ cells count and percentage, (flow cytometry, Facs Canto II, Becton Dickinson) CD4/CD8 ratio and plasma levels of interleukin 6, 10 (IL-6, IL-10), tumor necrosis factor (TNF) and interferon-gamma (IFN- $\gamma$ ) were measured using a sandwich-type immunoassay, ELISA (Biolegend). Serology for syphilis, HBV, and HCV will be repeated at week 24 and 48. If patients had an exacerbation of KS outside the scheduled visit they will be reevaluated with laboratory tests and study images.

A qualified phlebotomist will carry out blood sampling.

### **Primary outcome:**

Mortality by all causes at end of follow-up, 48 weeks, adjusted at least by age, gender, CD4, and viral load of HHV-8, primarily with a survival analysis by a Cox regression, but also with a logistic regression model.

### **Secondary outcomes:**

Total number of SIRS events (S-IRIS-KS and Non-S-IRIS-KS) in treated and control group. This is going to be done by a Poisson's models analysis adjusted by age, gender, coinfections, baseline: CD4, and viral load of HV8, C reactive protein, HIV VL, IL6, IL10, TNF, and IFN. We will compare mortality in patients with pulmonary KS between groups.

### **Vigilance of adverse events:**

Adverse events in treated and control group will be reported.

**Statistical analysis:**

The primary analysis is going to be as intention to treat, but as a secondary analysis also as per protocol analysis is going to be performed for mortality, and S-IRIS-KS.

**Ethical issues:**

Protocol and informed consent were reviewed and accepted by IRB from Instituto Nacional de Cancerología. (CEI/950/15No.15/03/INI)

First submission: 14 October 2014

First amendment: July 22, 2016

Second amendment. 25 April 2018

**TITLE: Valganciclovir Four Weeks Prior to cART
Initiation Compared to Standard Therapy for
Disseminated Kaposi Sarcoma**

NCT number: 03296553

DATE: November 30, 2019.

Statistical analysis

Sample size was calculated for a study power of 80% and an alpha of 0.05, with an estimated event rate (IRIS) in the control group of 40%, and in the treated group of 5%. The number estimated in each group was 19, for a total sample of 38 patients.

Descriptive statistics were performed, including the number of deaths, and episodes of S-IRIS-KS, in the CG and EG groups. Comparisons between EG and CG were performed, as intention-to-treat (ITT), and as per-protocol analysis, for the primary outcome of mortality attributed to S-IRIS-KS using Proportional-Hazard Cox models.

In addition, we compared the impact of treatment on repeated episodes of S-IRIS-KS by multivariate Poisson model and by the number of participants with at least one S-IRIS-KS event, as repeated events can occur in the same patient, and the total number of events may be due to a few very susceptible individuals.

Statistical models were adjusted by baseline CD4+, CD4+/CD8+ cell ratio, HHV-8 and HIV VL, plasmatic IL-6, CRP and by the presence of concomitant coinfections. Analyses were performed using Stata Statistical program.

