### **Hypothesis:**

In patients with AIDS and disseminated KS administration of valganciclovir as an anti-HHV-8 agent can diminish viral replication prior to administration of cART, and thus decrease the frequency of S-IRIS-KS with a subsequent reduction on S-IRIS-KS attributable mortality.

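### The stated 80% power is for IRIS (40% vs 5%), but the primary outcome in both documents is mortality, for which 19 per group gives about 64% power at 75% case fatality and 39% at 50%, if fatality is equal in both arms

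*SAP*

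**What the plan says.** **Sizing.** The SAP's opening paragraph sets power at 80% and alpha at 0.05 and sizes the trial "with an estimated event rate (IRIS) in the control group of 40%, and in the treated group of 5"%, which leads to 19 per group and 38 in total. The protocol (Sample Size) uses the same two rates and the same 19 per group but does not name the event. It adds: "This assumes a significant impact of treatment on S-IRIS-KS occurrence and its mortality".

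**Primary outcome.** The protocol (Primary outcome) has "Mortality by all causes at end of follow-up, 48 weeks", analysed mainly by adjusted Cox regression. The SAP compares the groups "for the primary outcome of mortality attributed to S-IRIS-KS using Proportional-Hazard Cox models".

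**IRIS.** The protocol (Secondary outcomes) lists "Total number of SIRS events (S-IRIS-KS and Non-S-IRIS-KS) in treated and control group". The SAP analyses repeated S-IRIS-KS episodes as an addition to the mortality comparison.

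**Link between the two.** The protocol (Hypothesis) expects valganciclovir to "decrease the frequency of S-IRIS-KS with a subsequent reduction on S-IRIS-KS attributable mortality". Of the severe form only, its IRIS criteria say: "This is the clinical picture associated with death".

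Neither document gives a mortality rate, a case fatality or a power for death.

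**The concern.** The only power figure in the plan belongs to an event that is not the primary outcome. A reader of the SAP meets 80% power and, in the next paragraph, a mortality primary outcome, and will naturally join the two.

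Death from IRIS cannot be more frequent than IRIS itself. Unless every case dies, the death rates lie below 40% and 5%, the absolute difference shrinks, and so does the power. Deaths from other causes, which count in the protocol's version of the outcome, dilute the contrast further.

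The interpretation of the result is at stake. If mortality does not differ significantly, the 80% would make that look informative when the design may have had little chance of detecting a real reduction.

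**Working it through.** **Inputs from the documents:** 40% vs 5%, alpha 0.05, 80% power, 19 per group, 48 weeks of follow-up.

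**Assumptions:** alpha two-sided (sidedness is not stated); case fatality *f* equal in both arms; background mortality *b* equal in both arms and independent of IRIS death; constant hazards; no dropout; unadjusted comparison. The documents give neither *f* nor *b*, so both are shown as ranges.

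**1. The plan's own figure.** With unpooled variance,

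n = (1.960 + 0.842)² × (0.40×0.60 + 0.05×0.95) / 0.35² = 18.4, rounded up to 19.

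The arcsine formula gives 18.6, also 19. The sample size is correct for 40% vs 5%.

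**2. Attributed death.** Death rates are 0.40*f* and 0.05*f*. Expected deaths in both arms together are 19 × 0.45*f*. Log-rank power is from 100,000 simulated trials per row; the chi-square (uncorrected) and Fisher columns are exact.

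| Case fatality | Death rates | Expected deaths | Log-rank | Chi-square | Fisher |
|---|---|---|---|---|---|
| 100% | 40% vs 5% | 8.6 | 80% | 80% | 68% |
| 75% | 30% vs 3.75% | 6.4 | 64% | 63% | 48% |
| 50% | 20% vs 2.5% | 4.3 | 39% | 39% | 22% |
| 25% | 10% vs 1.25% | 2.1 | 9% | 9% | 3% |

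The last row can be checked by hand. With 19 per group, 3 deaths against 0 gives a chi-square of 3.26 and 4 against 0 gives 4.47, so at least 4 against 0 is needed to pass 3.84. With one death in the treated group, 6 against 1 is needed (4.38). At 10% vs 1.25%, the chance of 4 or more control deaths is 0.115 and of no treated death 0.9875¹⁹ = 0.787, product 0.091. Adding 6 or more against 1 (0.0086 × 0.189 = 0.002) brings it to about 9%.

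**3. All-cause death.** Each rate becomes 1 − (1 − IRIS death rate)(1 − *b*). For example, *f* = 75% and *b* = 10% give 1 − 0.70×0.90 = 37% vs 1 − 0.9625×0.90 = 13.4%. Log-rank power:

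| Background mortality | *f* = 100% | 75% | 50% | 25% |
|---|---|---|---|---|
| 5% | 68% | 49% | 29% | 11% |
| 10% | 58% | 40% | 23% | 10% |
| 20% | 44% | 28% | 16% | 8% |

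**4. If treatment also lowers case fatality** (no background deaths), log-rank power is:

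- 30% vs 0%: 87%
- 30% vs 1%: 80%
- 25% vs 0%: 74%
- 20% vs 0%: 55%

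The 30% vs 1% case means 75% fatality in controls (0.30/0.40) and 20% in treated patients (0.01/0.05).

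**5. Choice of method.** The Schoenfeld formula gives 81% at 75% fatality and 61% at 50%; Freedman's gives 53% and 38%. Both are large-sample approximations, and here there are about 4 to 6 deaths with a hazard ratio near 0.11. The simulation and the exact chi-square calculation agree with each other and are the better guide.

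**The case against.** The strongest reply is that the protocol's sizing paragraph mentions an impact on S-IRIS-KS and on its mortality, so the sponsor may have expected treatment to lower fatality as well as incidence. In that case power for death could reach 80% to 87% (step 4). This is possible, and it means the power is unknown rather than certainly low. But the sentence gives no death rate, and the Hypothesis derives the mortality reduction from fewer S-IRIS-KS cases, which makes equal fatality the natural base case. If 40% and 5% were meant as death rates, the SAP's IRIS label is wrong and needs correcting anyway.

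Three further points are fair:

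- **Assumed inputs.** The 64% and 39% depend on assumed fatalities and a two-sided test. A one-sided test would give about 77% and 57%, still below 80%.
- **Test used.** The planned Cox models are covariate-adjusted and the figures here are not. That does not rescue the 80%: with 4 to 6 deaths, models with so many covariates could not be fitted reliably.
- **Which IRIS.** Severe IRIS is the more natural reading of the sizing event, given the protocol's Objective and Sample Size text. If any IRIS was meant, the fatal share is lower still, but the conclusion does not need that reading.

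Finally, the SAP is dated November 2019 and written in the past tense, so the design can no longer change. What can still change is how the mortality result is described.

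**Conclusion.** The concern holds. The 80% power applies to IRIS at 40% vs 5%, and neither document supports carrying it over to mortality. With 19 per group and equal case fatality of 25% to 75%, power is about 9% to 64% for the SAP's attributed mortality. It is about 8% to 49% for the protocol's all-cause mortality with 5% to 20% background deaths. Under equal fatality, 80% is kept only if essentially every IRIS case dies and there are no other deaths. It can also be reached if treatment cuts case fatality steeply, which the plan does not state.

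The ranges rest on assumed fatality and background mortality, a two-sided 0.05 test, no dropout and no covariate adjustment. The mismatch itself rests only on the documents' text. It must be fixed because it governs how a non-significant primary result may be read.

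**What to change.** In the protocol's Sample Size section and the SAP's sample-size paragraph:

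1. State that the 80% refers to the IRIS event at 40% vs 5%, and not to mortality. For clarity, the sponsor should say whether that event is any IRIS or S-IRIS-KS, and which formula was used.
2. Add the power with 19 per group for whichever mortality outcome is kept as primary, over a stated range of case fatality and, for all-cause death, of background mortality. If lower fatality under treatment was assumed, give the rates.
3. Describe the mortality comparison as having limited power, so that a non-significant result is not reported as evidence of no benefit.

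The cost is a few sentences and one small table. No extra patients and no change of endpoint or analysis are needed. The stated power for the primary outcome will look less favourable.

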### **Randomization**

Patients will be randomized by blocks of ten; the assigned group written in closed envelopes:

Experimental Group 1 (EG) will receive valganciclovir 900 mg twice daily for 48 weeks and initiate cART at week 4 after randomization.

Control Group 2 (CG) will start cART immediately according to current Mexican Guidelines.

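### The SAP makes S-IRIS-KS-attributed death primary where the protocol makes all-cause death primary, and the SAP's outcome cannot count experimental-group deaths before cART

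*SAP*

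**What the plan says.** The protocol's Primary outcome section names "Mortality by all causes at end of follow-up, 48 weeks", analysed mainly by adjusted Cox regression and also by logistic regression. Its Statistical analysis section makes intention to treat primary and says "also as per protocol analysis is going to be performed for mortality, and S-IRIS-KS".

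The SAP reports group comparisons, both ITT and per protocol, "for the primary outcome of mortality attributed to S-IRIS-KS using Proportional-Hazard Cox models". It mentions the total number of deaths only among the descriptive statistics.

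Death attributable to S-IRIS-KS does appear in the protocol's Objective and Hypothesis. It is not listed under Primary outcome or Secondary outcomes.

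The protocol's criteria section says that severe IRIS "Is defined as an abrupt clinical deterioration after cART initiation", with at least two clinical and three laboratory criteria, and adds: "This is the clinical picture associated with death". Under Randomization, controls start cART at once and the experimental group is to "initiate cART at week 4 after randomization". The Blinding section says that the trial is open label.

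The Ethical issues section gives only dates for the amendments: "First amendment: July 22, 2016" and "Second amendment. 25 April 2018".

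**The concern.** Two documents for one trial name different primary outcomes, and the later one does not acknowledge the difference. That alone needs reconciling.

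The SAP's outcome also treats the groups unequally by construction. The strategy under test includes a four-week delay of cART, so deaths during that delay are part of what the trial should measure. The SAP's primary comparison cannot register them in the experimental group. Keeping the ITT analysis set does not help: the patients stay in the analysis, but their early deaths are not events.

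Attribution adds a further weakness. The protocol defines an S-IRIS-KS episode, but neither document gives a rule linking a particular death to an episode, and no blinded adjudication is described. All-cause mortality needs no such judgement.

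**Working it through.** **1. Which early deaths can count.** This follows from the protocol's Randomization and criteria sections.

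| Death in weeks 0–4 | cART started? | Can be S-IRIS-KS death (SAP primary)? | Counts as all-cause death (protocol primary)? |
|---|---|---|---|
| Control | Yes | Yes, if the criteria are met | Yes |
| Experimental, before cART | No | No | Yes |

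The SAP states no time origin and no handling of competing deaths that would remove this difference.

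**2. The plan's own figure.** For 40% v 5%, 80% power and alpha 0.05 (taken as two-sided), the unpooled formula gives n = (1.960 + 0.842)² × (0.40×0.60 + 0.05×0.95) / 0.35² = 18.42, rounded up to 19 per group. This matches the plan. The pooled formula needs 22. The SAP labels these rates as IRIS rates. The protocol's Sample Size section leaves the event unnamed and says that an effect on both S-IRIS-KS and its mortality is assumed.

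**3. How many deaths might fall in weeks 0–4.** The documents give no death rate, so 48-week mortality m is an assumption. With constant hazard, p4 = 1 − (1 − m)^(4/48). Expected deaths are 19 × p4, the chance of at least one is 1 − (1 − p4)^19, and the share of deaths after week 4 is 1 − p4/m.

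| m | p4 | Expected deaths in 19 | Chance of at least one | Share of deaths after week 4 |
|---|---|---|---|---|
| 10% | 0.0087 | 0.17 | 15% | 0.913 |
| 20% | 0.0184 | 0.35 | 30% | 0.908 |
| 30% | 0.0293 | 0.56 | 43% | 0.902 |
| 40% | 0.0417 | 0.79 | 55% | 0.896 |

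If treatment had no effect and every death after cART start were attributable, the experimental group could count about 90–91% of the deaths that the control group could.

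**4. What one death does.** The test is two-sided Fisher with 19 per group, an unadjusted stand-in for the adjusted Cox model. Counts are hypothetical, experimental v control.

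| Deaths added | From | To |
|---|---|---|
| One, experimental only | 0 v 5 (p=0.046) | 1 v 5 (p=0.18) |
| One, experimental only | 0 v 6 (0.020) | 1 v 6 (0.090) |
| One, experimental only | 1 v 8 (0.019) | 2 v 8 (0.062) |
| One, experimental only | 0 v 7 (0.008) | 1 v 7 (0.042) |
| One, experimental only | 0 v 8 (0.003) | 1 v 8 (0.019) |
| One in each group | 0 v 5 (0.046) | 1 v 6 (0.090) |
| One in each group | 1 v 7 (0.042) | 2 v 8 (0.062) |
| One in each group | 0 v 6 (0.020) | 1 v 7 (0.042) |
| One in each group | 1 v 8 (0.019) | 2 v 9 (0.029) |
| One in each group | 2 v 9 (0.029) | 3 v 10 (0.038) |

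Some splits cross 0.05 and others do not.

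**5. Power cost of all-cause mortality.** For illustration, treat 40% and 5% as IRIS-death rates p and add other deaths at rate o in both groups: total rate = 1 − (1 − p)(1 − o), with 19 per group.

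| o | Control v experimental | Power, unpooled | Power, pooled |
|---|---|---|---|
| 0% | 40% v 5% | 81% | 75% |
| 5% | 43% v 9.75% | 71% | 65% |
| 10% | 46% v 14.5% | 61% | 56% |
| 20% | 52% v 24% | 46% | 42% |

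**The case against.** The strongest reply is that the SAP's outcome matches the aim in the protocol's Objective and Hypothesis, so the protocol is itself inconsistent. That is true. But the protocol has a section that designates the primary outcome, with its time point and models, and a general aim does not override it.

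The SAP also does not say that the all-cause analysis was dropped. It is a short document, and silence is weaker than withdrawal. Even so, the outcome it calls primary is a different one.

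On size, a spurious ratio near 0.9 is small beside a planned 40% v 5%. The exclusion of patients with APACHE II above 15 may reduce early deaths. A control death in weeks 0–4 counts only if tied to a qualifying episode. The Fisher counts are hypothetical. These points stand: they limit what can be claimed about size but leave the direction of the asymmetry unchanged.

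The content of the amendments was not supplied, so one of them may have explained the change. No undisclosed switch should be inferred.

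**Conclusion.** The concern holds. The two primary outcomes differ and the supplied documents give no reason. The pre-cART asymmetry follows directly from the protocol's definition of S-IRIS-KS and its cART timing. Confidence is high on the discrepancy and on the direction of the asymmetry taken alone, which favours the experimental group.

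The size is not known. The illustrative ranges rest on assumed mortality, constant hazard and, for the 90–91% figure, full attribution of deaths after cART. The net effect of returning to all-cause mortality also depends on the number of non-IRIS deaths in each group, which the documents do not give. With 19 per group the choice of outcome can change the conclusion, but it need not.

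**What to change.** In the SAP:

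- Make all-cause mortality from randomisation to week 48, by ITT, the primary comparison, as in the protocol's Primary outcome section. State randomisation as time zero.
- Keep S-IRIS-KS-attributed mortality as a secondary outcome. Report cumulative incidence with other deaths as a competing event, and state the rule that links a death to an episode. A cause-specific Cox model is also a valid choice.
- Tabulate deaths in weeks 0–4 by group.
- State that the SAP labels 40% v 5% as IRIS rates, so 80% power is not shown for all-cause mortality.

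The SAP is written in the past tense. If the analysis has already been run, report all-cause mortality as the protocol's primary outcome and label the attributed outcome as a change. The Objective and Hypothesis can stay as they are, with attributed mortality serving them as a secondary outcome.

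The cost is SAP wording and one extra table. No new data are needed, because the protocol already plans a survival analysis of all deaths. The drawback is the loss of power from non-IRIS deaths shown in step 5, which should be disclosed.

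### The Poisson model for repeated S-IRIS-KS episodes has no stated variance correction, although the SAP allows that a few patients may produce most events; a minor, secondary-outcome fix

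*SAP*

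**What the plan says.** The SAP (Statistical analysis) compares the arms on "repeated episodes of S-IRIS-KS by multivariate Poisson model and by the number of participants with at least one S-IRIS-KS event". It gives its reason at once: events can recur in one patient, and "the total number of events may be due to a few very susceptible individuals". Models are adjusted for seven baseline variables: CD4+, CD4+/CD8+ ratio, HHV-8 load, HIV load, IL-6, CRP and coinfections.

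The protocol (Secondary outcomes) names a different count, "Total number of SIRS events (S-IRIS-KS and Non-S-IRIS-KS) in treated and control group", and says "This is going to be done by a Poisson's models analysis adjusted by age, gender, coinfections", followed by further baseline covariates. It does not mention the at-least-one-event comparison.

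Neither document states a scale parameter, robust or clustered standard error, negative binomial model or random effect. Neither says what is done if an arm has no events, or which of the SAP's two comparisons leads.

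**The concern.** A Poisson model takes the variance of each patient's count to equal its mean, given the covariates. A few very susceptible patients are exactly what breaks that. If the variance is φ times the mean, the default standard error is too small by a factor √φ, and p-values and intervals look better than they should.

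This is a secondary outcome and does not touch the mortality analysis. It does bear on the trial's hypothesis, which is that valganciclovir before cART lowers the frequency of severe IRIS.

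**Working it through.** **Inputs from the documents.** 19 patients per arm, event rates 40% (control) and 5% (treated), alpha 0.05, power 80% (SAP; Protocol, Sample Size).

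**Assumptions, not in the documents.** Alpha is two-sided. The 40% and 5% are read as the proportions of patients with at least one event. Susceptibility varies between patients as a gamma frailty with variance v. Episodes per patient are capped at two or three, because the protocol says of severe IRIS that "This is the clinical picture associated with death", so long runs of episodes are unlikely.

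**1. The plan's own figure.** Two proportions, unpooled variance: (1.960 + 0.842)² × (0.40 × 0.60 + 0.05 × 0.95) / 0.35² = 7.85 × 0.2875 / 0.1225 = 18.4, rounded up to 19. The figure reproduces. It concerns a proportion, so the documents give no planning figure for episode counts.

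**2. How much extra variance clustering creates.** To keep the proportion affected at p, the mean count is μ = ((1 − p)^(−v) − 1)/v, and variance/mean is 1 + vμ before capping. At p = 0.40:
- no clustering: μ = −ln 0.60 = 0.511, variance/mean 1
- v = 1: μ = 0.667, variance/mean 1.67
- v = 2: μ = 0.889, variance/mean 2.78

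Capping reduces this. Capped at three, affected patients average 1.6, 1.8 and 2.2 episodes at v = 1, 2 and 4. Capped at two, they average 1.4, 1.5 and 1.7.

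**3. Type I error of the default Wald test.** 19 per arm, no treatment effect, nominal 5%:

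| Setting | Default Poisson |
|---|---|
| 40% affected, no clustering | 4% |
| 40% affected, at most two episodes, v = 1 to 4 | 4-6% |
| 40% affected, at most three episodes, v = 1 to 4 | 8-12% |
| 40% affected, no cap, v = 0.5 and 1 | 7% and 11-12% |
| 22.5% affected (midpoint of 40% and 5%), at most three, v = 1 and 2 | 4% and 6% |
| 40% affected, at most three, v = 1 to 4, seven covariates explaining none of the susceptibility | 8-9% |
| The same, covariates explaining half | 5-7% |

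Scaling by the Pearson dispersion, floored at 1, gives about 5% or less in every row. The covariate rows rest on 2,500 trials with a log-normal frailty, so their simulation error is about √(0.08 × 0.92/2500) = 0.5 percentage points. The other rows rest on 40,000 trials per setting.

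**4. What scaling does to one invented data set.** Control: 3, 3, 2, 2, 1, 1, 1, 1 and eleven zeros (14 episodes). Treated: five patients with one each.
- Default: rate ratio 5/14 = 0.36; standard error of its log √(1/14 + 1/5) = 0.521; interval 0.13-0.99; p = 0.048.
- Pearson dispersion: control (30 − 14²/19)/(14/19) = 26.71; treated (5 − 5²/19)/(5/19) = 14.00; (26.71 + 14.00)/36 = 1.13.
- Scaled: standard error 0.521 × √1.13 = 0.554; interval 0.12-1.06; p = 0.063.
- A robust variance on the same data gives p = 0.039, so the correction used has to be named in advance.

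**5. A treated arm with no events.** At 5% per patient, 0.95^19 = 0.377, or 38% of trials. The log rate ratio is then infinite and the Wald test is undefined. This happens with no clustering at all.

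**The case against.** **The SAP already guards against this.** The words on susceptible individuals are its reason for adding the at-least-one-event comparison, which repeat episodes cannot distort. This stands as a partial safeguard. It does not correct the count model's intervals, which will still be reported.

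**The SAP does not predict clustering.** A reader might infer that the authors expect it and ignored it. The text says only that it may occur, so the point is conditional.

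**The inflation may be negligible.** With at most two episodes per patient it is 4-6%, and covariates that explain half the susceptibility bring it to 5-7%. This stands, and it is why the point is minor. Covariates are not a dependable remedy, though. The planning rates imply about 19 × 0.40 + 19 × 0.05 = 8.6 affected patients, against eight coefficients with treatment.

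**The two comparisons might be thought to contradict each other.** A reader could infer that they will often give opposing results and that the patient-level test must therefore lead. That does not follow. In the example both favour treatment. Two different tests, one of them conservative, will often differ in significance without any clustering. Much of the remaining difference comes from the undefined Wald test when the treated arm has no events. A Fisher test in the lead would have about 68% power at 40% versus 5%, and it would be unadjusted. That is a trade-off for the sponsor, not an error in the plan.

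**Conclusion.** The omission is real: a count model with no stated variance correction, in a plan that itself raises the possibility of clustering. Default type I error would be about 8-12% if patients have up to three episodes and frailty variance is 1 to 4. It is 4-6% if none has more than two, and lower than 8-12% where covariates explain part of the susceptibility. These sizes rest on assumed frailty variances and caps, because the documents give no episode counts per patient, so confidence is medium.

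The undefined rate ratio in a treated arm without events is a separate gap. Its 38% follows from the planning rates, if 5% is the proportion of patients affected.

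The documents do not support saying that the SAP overlooks recurrence or that its severe-IRIS result would be unsound. This is a minor correction to a secondary analysis.

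**What to change.** Add to the SAP:
1. Fit the count model with a Pearson-scaled variance (Stata glm, family(poisson) scale(x2)). If the estimated dispersion is below 1, use 1; state this as a rule, because scaling alone would otherwise narrow the intervals. Pearson scaling is preferable to a robust variance at this size. In uncapped simulations with variance/mean of 1.5 to 3, the robust Wald test still rejected in about 6-8% of no-effect trials.
2. If an arm has no events, take the p-value from a named likelihood-ratio or permutation test. An unscaled likelihood-ratio test solves the zero-event problem but not clustering: in the same simulations it rejected in 11% of no-effect trials at variance/mean 1.5. A permutation test avoids that, but it is unadjusted and should respect the blocks of ten used for randomisation.
3. Report the at-least-one-event comparison beside the count model, and state which of the two leads. That choice is the sponsor's.

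The cost is a few sentences and one software option, with no new data. Count-model intervals become wider on the log scale, by a median factor of 1.02-1.09 if no patient has more than two episodes and 1.14-1.31 if none has more than three (v = 1 to 4).
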